5.0 Procedures Involved*

Enrollment Procedures. Enrollment in this study may occur at any time during the recruitment period. Potential participants recruited utilizing the OneFlorida Data Trust will receive a “text-in” number, in which interested persons will be able to text-in to receive instructions for screening and enrollment. Potential participants through the OneFlorida Data Trust who do not “opt-out” of being contacted could also be directly contacted by the study team to be informed of the study and screening/enrollment options for preliminary eligibility.

Screening and enrollment may occur on the same day, as long as the appropriate VL and ART regimen data are appropriately obtained. If a participant is determined to be eligible for the study, a unique Qualtrics link will be sent to the participant for submitting proof of HIV VL ≥ 200 copies/mL and ART regimen. After final eligibility is determined, study staff sends the potential participant the SMART enrollment link, which contains the study

PROTOCOL TITLE: ATN 144 SMART

consent/assent form, HIPAA Authorization form, and the baseline web-based survey. These are programmed in Qualtrics by the REC. The baseline survey can be completed at the participant's convenience (ideally within 14 days before and 28 days after their scheduled assessment date). Upon completion of all portions of the enrollment link, participants are considered enrolled in SMART. Study staff will then randomize and stratify the participants into their respective intervention arms (CPS or SMS) for the first period of the study. Stratification is based on method of contraction: Perinatal vs Behavioral (and other).

Participants randomized to the CPS intervention group will speak with the AF to determine the start day and call time for intervention phone calls. This phone call should be completed within 30 days from entry. Participants randomized to the SMS intervention will speak with the Project Coordinator (PC) to identify the start day, timing, and content of the text messages they will begin receiving daily.

At each follow-up, participants will complete web-based surveys programmed in Qualtrics by the REC. A link to these computerized surveys will be sent to each participant by the REC and can be completed at the participant's convenience (ideally within 14 days before and 28 days after their scheduled assessment date). Participant VL data will need to be obtained before the study procedures for the respective assessment period is considered complete and the participant is compensated. Data files will be downloaded via Qualtrics by the Data Management Team of the REC. The REC will maintain a linkage of PID and subject name, and these will be stored in password protected files. These web-based surveys will take approximately 60-90 minutes to complete.

Randomization Process/Systems. Participants will be randomized at the end of their baseline assessment into one of two intervention conditions: (1) CPS or (2) SMS. Both intervention conditions will receive 3 months of intervention (i.e., 3 months of CPS or SMS). Each participant's condition will be tracked in REDCap. At the 3-month follow-up, a second stratified randomization will occur in blocks with 8 possible intervention trajectories as follows:

- CPS responders (VL <200 copies/mL) will be randomized to either 9 months of standard care (SC) or 3 months of CPS-T followed by 6 months of SC;
- CPS non-responders (VL \geq 200 copies/mL) will be randomized to 3 months of CPS-I or SMS-I followed by 3 months of CPS-T or SMS-T, respectively, and then 3 months of SC for both groups thereafter;
- SMS responders (VL <200 copies/mL) will be randomized to either 9 months of SC or 3 months of SMS-T followed by 6 months of SC; and
- SMS non-responders (VL \geq 200 copies/mL) will be randomized to 3 months of CPS-I or SMS-I followed by 3 months of CPS-T or SMS-T, respectively, and then 3 months of SC for both groups thereafter.

Participants who are unable to provide a valid HIV VL result at the 3-month time point have approximately 30 days to obtain a HIV VL performed at Quest Diagnostics or have a physician release this information to PRIDE. Participants who are unable to provide this

PROTOCOL TITLE: ATN 144 SMART

information within the timeframe i.e. 30 days after their 3 month follow-up assessment will be treated as non-responders to the intervention and will be re-randomized to an incentive arm. The 30 day window follows the same timeframe as the 30 day window for calls to begin following baseline.

Retention and Follow-up. The REC will have automated procedures to communicate with participants about remembering to complete their surveys, and also to complete VL testing. Participants will be reminded of upcoming study procedures, including VL blood draw logistics. The locator form will be reviewed with the participant during these reminder calls, and any changes will be noted. Multiple contact methods will be used for difficult to reach youth (e.g., alternate phone numbers, email, text messaging, family members, or friends and healthcare providers). We will have a mechanism in place for troubleshooting text-message bounce-backs and retaining hard to reach participants.

All participants are retained in the intervention regardless of their missing the 75% monthly requirement or missing several consecutive weeks. The incentive is provided only for the months that participants reach the 75% target. This is expected to increase the overall number of calls and SMS completed over the 3-month CPS-I and SMS-I interventions.

Study staff will use Trumpia to text participants during the duration of their participation in the study to remind them of upcoming follow-up visits. Participants will receive both an email and a text message reminder simultaneously. The text message will inform a participant that an email reminder was sent and will ask the participant to respond accordingly with a number notifying staff that they received the email, or if there are any problems. (e.g., “text back ‘1’ if you received the email or ‘2’ if you DID NOT receive the email.”). Study staff will utilize an Access database using an Application Program Interface connected to Trumpia’s secure server to track responses and respond to participants accordingly.

Specimen Collection. VL will be collected for baseline and follow-up assessments (i.e., months 3, 6, 9 and 12) for all participants. This is the only study component that cannot be completed by the participant online or by phone. Participants have several options for how they would like this data submitted to the REC.

VL measurements collected during screening or after will be used for the baseline assessment, as long as the remaining components of the baseline assessment are completed no later than 1 month from the VL collection date (exceptions to this must be approved by the REC).

Participants may submit VL test results from their standard care providers (at both SRV and non-SRV clinics) as long as they were measured using a level of detection of <200 copies/mL or below and the VL collection dates are within 6 months prior to screening or the baseline assessment, and within 2 weeks prior to or 4 weeks after all other study follow-up assessments. VL measurements using a level of detection ≥ 200 copies/mL will not be accepted. If participants have a standard care provider, but no VL test results

PROTOCOL TITLE: ATN 144 SMART

within the required window period, they may request a new VL test from their usual provider and invoice the REC.

If participants decide to obtain a copy of their standard care VL test results, they will be given two choices on how to submit their VL test results. The REC will inform the participant that they may take a picture of their newly obtained standard care VL test result using their personal cell phone and submit the picture through a secure Qualtrics online submission form. Participants may also request their providers directly send their newly obtained lab results to the REC. This option may require youth to provide a release of information (ROI) if one is not already in place.

If standard of care results are not available, participants who have access to a clinical SRV, but have not completed a VL test within the required window period may request a new VL test for research purposes. The REC will refer participants to a clinical SRV; participants do not need to be an existing patient or establish care at this clinic in order to complete this study component. This new test will be invoiced to the REC and not billed to the patient's insurance. Clinical care VL measurements can be used as long as they were measured using a level of detection of <200 copies/mL or below. VL measurements using a level of detection ≥ 200 mL will not be accepted. Participants should complete this VL test within 1 month of screening before the baseline assessment, and within 2 weeks of each follow-up assessment. The REC will contact providers to submit VL measurements via fax or Qualtrics.

Participants who cannot or do not wish to visit a medical provider may be referred to local Quest Diagnostics labs for VL testing. The REC will order and pay for these labs, and receive VL data directly via online.

One way the Privacy Rule protects the privacy of protected health information (PHI) is by generally giving individuals the opportunity to agree to the uses and disclosures of their PHI by signing an authorization form for uses and disclosures not otherwise permitted by the Rule.

The Privacy Rule establishes the right of an individual, such as a research subject, to authorize a covered entity to use and disclose their PHI for research purposes. This requirement is in addition to the informed consent to participate in research required under the Department of Health and Human Services (HHS) Protection of Human Subjects Regulations and other applicable Federal and State law.

Incentives and Compensation. Participants will be compensated up to \$500 total for completing all study assessments, not including compensation for completing the intervention. Participants will be compensated \$60 after completing the baseline survey and providing the proof of viral load. A \$10 increased compensation will be offered over time each time participants complete the survey and submit viral load results. We will also offer a \$10 bonus for participants who complete the survey within one week of the date is sent out and a \$10 bonus for participants who submit the viral load results within two weeks of the date link is sent out. See table below for a summary of the

PROTOCOL TITLE: ATN 144 SMART

compensation amounts for each study assessment. At the end of each month for participants in the CPS-I and SMS-I interventions, those participants who reach the 75% monthly adherence to calls/text responses will receive \$50. Compensation will be provided via electronic gift cards (e.g., Amazon, Target, or Walmart).

Baseline Assessment Compensation	\$ 80.00
Submission of the viral load result	\$ 30.00
Completion of the survey	\$ 30.00
Submitting the viral load result within two weeks of the screened eligible date (bonus)	\$ 10.00
Completing the survey within one week of the date is sent out (bonus)	\$ 10.00
3-Month Assessment Compensation	\$ 90.00
Submission of the viral load result	\$ 35.00
Completion of the survey	\$ 35.00
Submitting the viral load result within two weeks of the date link is sent out (bonus)	\$ 10.00
Completing the survey within one week of the date is sent out (bonus)	\$ 10.00
6-Month Assessment Compensation	\$ 100.00
Submission of the viral load result	\$ 40.00
Completion of the survey	\$ 40.00
Submitting the viral load result within two weeks of the date link is sent out (bonus)	\$ 10.00
Completing the survey within one week of the date is sent out (bonus)	\$ 10.00
9-Month Assessment Compensation	\$ 110.00
Submission of the viral load result	\$ 45.00
Completion of the survey	\$ 45.00
Submitting the viral load result within two weeks of the date link is sent out (bonus)	\$ 10.00
Completing the survey within one week of the date is sent out (bonus)	\$ 10.00
12-Month Assessment Compensation	\$ 120.00
Submission of the viral load result	\$ 50.00
Completion of the survey	\$ 50.00
Submitting the viral load result within two weeks of the date link is sent out (bonus)	\$ 10.00
Completing the survey within one week of the date is sent out (bonus)	\$ 10.00
Total Compensation (upon completion of all 5 assessments)	\$ 500.00

Measures. Baseline data collections should be completed all within the same day, and ideally no later than 7 days after the beginning of the baseline. Follow-up data collections should be collected up to 14 days prior to target date and up to 28 days after the target date. Due to COVID-19 pandemic, 12-month assessment window will be extended to 90 days. Those who are overdue for 12-month assessment will be allowed to complete the CASI and submit the VL after their window is closed. These participants will receive 90 days extension to complete the last component of the study. The REC Data Management Team will monitor reports of when participants are due for follow-up assessments. Self-report measures will be collected via a link to Qualtrics which can be accessed via smartphone, laptop, or PC. Site characteristics, including resources and supports available for non-adherent youth living with HIV, will be recorded into a Qualtrics survey and managed by the REC.

PROTOCOL TITLE: ATN 144 SMART

[figure not shown]
Web-based CASI Measures	Baseline	Follow-Up
Demographics		
Demographics/Socioeconomic Characteristics (ATN)	X	
Primary Outcomes		
HIV Positive Cascade: Medication Adherence Variables	X	X
Viral Load	X	X
Other Self-Reported Measures		
HIV Positive Cascade: Other Participant Characteristics	X	X
Self-Efficacy for Medication Adherence	X	X
Sexual Risk Behavior Questionnaire (harmonized + additional questions)	X	X
Additional Self-Management Measures		
Substance Use: ASSIST	X	X
PHQ-8 (Depression)	X	X
GAD7	X	X
PROMIS: Emotional Support, Informational Support, Instrumental Support, Companionship, Social Isolation	X	X
BRIEF-A: Plan/Organize and Task Monitor Scales; Plan/Organize and Shift Scales; Behavioral Regulation Subscales (Inhibit, Self-Monitor)	X	X
PAM (Patient Activation Measure)	X	X
Modified Healthcare Access Measure	X	X
HIV Positive Cascade Biomedical Data – Chart Abstraction		
HIV Positive Cascade Biomedical Data (harmonized + ART Regimen)	X	X
Supplement Measures		
HIV Stigma Scale	X	X
Knowledge of HIV Treatment Scale	X	X
Internalized Homophobia Scale	X	X

Sub-Study:

PROTOCOL TITLE: ATN 144 SMART

Study Design. To collect pilot data on the development and implementation of DBS procedure, this study seeks to conduct a mixed-method analysis to examine suitability, feasibility and acceptability of utilizing DBS for obtaining VL data. We will conduct recruitment for this study by reaching out to contacts who have been previously screened and not currently enrolled in SMART due to enrollment criteria or those who were unable to complete the components of the enrollment phase. We will develop survey measures and structured interview guide to collect both quantitative and qualitative data.

[figure not shown]
Figure 1. Project DABS' three study components.

Study Assessments

Hemaspot™-HF Blood Sampling Kit. Once the protocol team has received the subject's consent/assent to participate, the protocol team will mail the HemaSpot™-HF blood sampling kit to the address provided by the participant. The HemaSpot-HF collection kit is a cartridge with absorbent paper covered by a surface with a small spot to direct blood onto the paper. After drawing 3 drops of blood, the paper is sufficiently saturated; a desiccant within the cartridge rapidly dries the blood to preserve it for transit to the laboratory, which can occur at ambient temperature. The HemaSpot cartridge will be placed within appropriately labeled specimen packaging and returned to the PRIDE Health Research Consortium at Hunter College with prepaid mailing labels. After receiving kits, study staff will store samples to be sent to the laboratory for testing in batches. The kit contains instructions on how to perform the blood collection and properly store and handle the kit (see below). Participants will also receive a brief survey that contains an instructional video along with the kits received and sent dates to allow for more accurate tracking and monitoring of the samples in transit. The Caliendo Molecular Laboratory at the Miriam Hospital in Rhode Island will then perform a quantitative analysis of VL using the participant's DBS sample. We will use the AmpliPrep/COBAS TaqMan HIV-1 Test, v2.0 assay to analyze samples collected.

Figure 2. Spot*On Sciences' HemaSpot™-HF blood collection sampling kit instructions.

Online Computer Assisted Self-interviewing (CASI). The protocol team will send an online CASI questionnaire, supported by the Qualtrics platform, via a hyperlink to the email and phone number provided by the subject. The online CASI will ask questions pertaining to the following: demographics, modules on suitability, feasibility, and acceptability of using DBS, social determinants of health, HIV cascade, and the last section focused on feedback for future trials.

Web-based CASI Measures	Baseline
Section A: Demographics (Aims 1, 2, and 5)	
ATN Standard Domain: Demographic Characteristics	X
Section B: Suitability, Feasibility, and Acceptability (Aim 1)	
Module 1: Suitability	
Intervention Appropriateness Measure (IAM)	X
Module 2: Feasibility	
Feasibility of Intervention Measure (FIM)	X

PROTOCOL TITLE: ATN 144 SMART

At-Home Dried Blood Spots Testing Usability Scale	X
Psychometric Analysis of the Perceptions of At-Home DBS Testing Questionnaire	X
Module 3: Acceptability	
Post-test Questionnaire on Acceptability and Preference of HIV Self-testing	X
Acceptability of Intervention Measure (AIM)	X
Section C: Social Determinants of Health (Aim 2)	
Module 1: Economic Stability	
Module 2: Education	
Module 3: Health and Health Care	
Health Care Utilization	X
Medical Research Distrust Scale	X
Module 4: Neighborhood and Built Environment	
Module 5: Social and Community Context	
HIV Stigma Scale	X
Experiences of Discrimination Scale	X
Section D: HIV Cascade (Aims 2 and 5)	
ATN Standard Domain: HIV Positive Cascade Participant Characteristics	X
SMART Self-Efficacy for Medication Adherence	X
Section E: Feedback for Future Trials	

Qualitative Interview. After the protocol team has received both completed HemaSpot™-HF blood collection sampling kit and online CASI from the subject, the protocol team will invite the subject via email, phone, or text, to participate in a qualitative phone interview aimed to gather the subject's thoughts on the suitability, acceptability and feasibility of the at-home blood sampling kit to determine the kit's utility as a VL monitoring and self-management tool for YLH. Completion of the qualitative interview concludes the subject's participation in this study.

Qualitative Interview Measures. Qualitative interview measures assess the suitability, acceptability, and feasibility of the adoption and use of the at-home DBS; anticipated barriers and facilitators of receiving at-home DBS collection kits; perspectives on implementation and recommendations on the delivery and pickup methods; cost and compensation; perspectives on implementation and engagement of participants; and

PROTOCOL TITLE: ATN 144 SMART

suggestions for future trials (see Appendix for the qualitative interview guide). The PRIDE Hunter Team will be responsible for conducting the qualitative interviews, audio recordings, and coding the data.

Referral to ATN 144 SMART. Subjects that produce an unsuppressed VL (≥ 200 copies/mL) could potentially join ATN 144 SMART as a subject. The protocol team will notify the subject of their lab result via phone and/or email and offer them the opportunity to enroll in ATN 144 SMART, a study aimed to assist YLH adhere to their ART so that they may achieve a suppressed VL (< 200 copies/mL). The subject will then follow ATN 144 SMART's study procedures if enrolled, which includes providing VL lab results every 3 months. If viable, the HemaSpotTM-HF blood sampling kit could potentially serve as a mechanism for collecting VL data for these subjects during ATN 144 SMART's retention phase. This referral will be offered at the end of their participation in this study. A participant cannot be concurrently enrolled in DBS and SMART.

Compensation. Subjects will receive \$20.00 compensation for successfully completing and mailing the DBS sampling kit and \$20.00 compensation for completing the online CASI and the qualitative phone interview. Subjects can therefore receive up to \$40.00 total compensation for completing all study assessments. Subjects will receive compensation in the form of an electronic gift card sent directly to the email they provide.

6.0 Data and Specimen Banking*

Data for Future Use

Participants consent to these procedures as part of the consent/assent process.

The research team, authorized staff, and government agencies that run this type of research may have access to research data and records in order to check on the research. Research records given to approved researchers will be de-identified. If a researcher requests the data, they will be granted special permission from the Research Compliance Administrator. Data collected during this research study may be used for future research purposes. The data stored will be de-identified.

Data that cannot be linked to participants (i.e., de-identified data) will be kept indefinitely; this data will be saved for future use and may be shared with other researchers.

Biological samples collected for the purposes of this study will not be used to conduct any future research. They will be destroyed after analysis is completed.

At the end of the study data collected will be made available, in accordance with the NIH Data Sharing Policy (http://grants.nih.gov/grants/policy/data_sharing). These data will be saved for future use and may be shared with other researchers. By participating in this study, you are agreeing to allow us to save and share your data anonymously.

PROTOCOL TITLE: ATN 144 SMART

Sub-Study:

Data Banking. Participants consent to these procedures as part of the consent/assent process. Data collected during this research study may be used for future research purposes. The data stored will be de-identified. Data that cannot be linked to participants (i.e., de-identified data) will be kept indefinitely; this data will be saved for future use and may be shared with other researchers without additional informed consent. The research team, authorized staff, and government agencies that run this type of research may have access to research data and records in order to check on the research. Research records given to approved researchers will not have identifying data. Publications and/or presentations that result from this study will not include the identifying data.

At the end of the study data collected will be made available, in accordance with the NIH Data Sharing Policy (http://grants.nih.gov/grants/policy/data_sharing). These data will be saved for future use and may be shared with other researchers. By participating in this study, participants are agreeing to allow us to save and share their data anonymously.

Specimen Banking. This study will not bank the DBS specimens for future use. Biological samples collected for the purposes of this study will not be used to conduct any future research. They will be destroyed after analysis is completed.

7.0 Sharing of Results with Subjects*

If participants go to Quest Diagnostics for VL testing, the research team will share with them the lab results produced by Quest. These results are not shared with any other individuals.

Sub-Study: The research team will share with subjects their VL lab results produced from the HemaSpot™-HF blood collection device. The protocol team will not share these results with any other individuals. Participants will receive their VL results by phone and may request a written copy be emailed to them. The protocol team will develop phone/email templates for sharing both detectable and undetectable results. The templates will include a brief introduction of the research staff delivering the results followed by either detectable or undetectable VL results and the meaning of those results. For those who had undetectable VL, no further step is needed. For those who had detectable VL, referral to SMART as well as any necessary referrals will be provided. Participants will also be recommended to follow up with health care provider.

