Secondary Objective(s)	
 • Conduct an exploratory evaluation of tapering the intensity of CPS and SMS (among responders) vs. termination after completion of the 3-6 month intervention to determine if this improves the durability of intervention effects. • Explore the relative effectiveness and cost-effectiveness of the individual intervention sequences embedded within the SMART design for responders and non-responders. • Assess the five components of the Self-Management Model and how these components vary over time, are directly improved by the intervention, and mediate intervention effects. • Assess barriers and facilitators to the implementation and sustainment of intervention sequences in adolescent HIV care settings using mixed methods (Exploration, Preparation, Implementation, and Sustainment [EPIS] surveys, qualitative interviews, fidelity measurements and sequential analysis). 
Sub-study:
 
 1. Examine barriers and facilitators of using DBS collection for VL monitoring and expand access to VL monitoring for HIV-positive youth between 15-24 years old. 2. Adapt VL collection methods (i.e., construction and distribution of at-home testing kits and surveys, tracking and monitoring testing kit completion, tracking and monitoring at-home survey completion) for DBS in this population. 3. Use a central laboratory to measure VL and evaluate the accuracy and lower limit of detection of a DBS. Currently, the lower limit is estimated at 500 to 800 copies/mL. This is not consistent with the latest definition of VL below detection (e.g., 200 copies/mL). Explore utilizing DBS collection to screen and monitor VL for ATN 144 SMART and future protocols.
Research Intervention(s)	
The intervention will consist of CPS or SMS. CPS will be provided by an adherence facilitator (AF) who will assess if participants have taken their antiretroviral therapy (ART) medication(s) and provide brief problem solving support. SMS will act as a reminder to participants to take their

PROTOCOL TITLE: ATN 144 SMART

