The primary aim of this sub-study “ATN 144b Dried At-Home Blood Science” (Project DABS) is to leverage our current ATN 144 SMART recruitment and screening methods and patient population to develop and test DBS implementation procedure to promote home-based DBS collection and change the landscape of adherence research in youth living with HIV. Additionally, if feasible, DBS collection implementation may enhance ATN 144 SMART protocols for obtaining VL, both at enrollment and follow-ups. DBS

PROTOCOL TITLE: ATN 144 SMART

collection has the potential to help identify additional youth who are eligible for ATN 144 SMART, thereby increasing enrollment in this difficult patient population, and aid in improving retention for those who do not provide VL via a clinic or testing facility.

Specific Aims:

1. Assess the suitability, feasibility and acceptability of using DBS collection to obtain timely data on VL monitoring for HIV-positive youth between 15-24 years old.
2. Examine barriers and facilitators of using DBS collection for VL monitoring and expand access to VL monitoring for HIV-positive youth between 15-24 years old.
3. Adapt VL collection methods (i.e., construction and distribution of at-home testing kits and surveys, tracking and monitoring testing kit completion, tracking and monitoring at-home survey completion) for DBS in this population.
4. Use a central laboratory to measure VL and evaluate the accuracy and lower limit of detection of a DBS. Currently, the lower limit is estimated at 500 to 800 copies/mL. This is not consistent with the latest definition of VL below detection (e.g., 200 copies/mL).
5. Explore utilizing DBS collection to screen and monitor VL for ATN 144 SMART and future protocols.

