Use of DBS technology, a method introduced by the World Health organization (WHO) guidelines in 2015 for routine VL monitoring of HIV-positive individuals on ART^{1,2} is currently underutilized in the United States. HIV biomarker, VL testing, has been increasingly recognized as the gold standard for monitoring treatment efficacy and detecting treatment failure.³ According to a systematic review of 13 articles evaluating the performance of DBS samples, DBS is still an emerging method for monitoring VL and has been mostly used for detecting HIV.³ Only two studies have found the lower detection limit to be 550 and 800 copies/mL.³ More recently, a study of 205 young adults with HIV living in the Chicago metropolitan area reported a significant percent (34%) of subjects with a detectable VL at the time of study visit self-reported an undetectable VL at their last medical visit.⁴ However, performing traditional serological testing requires youth to schedule an appointment either with their primary care provider or a laboratory such as Quest Diagnostics to extract the serum from blood specimens. In the context of a research study such as ATN 144 SMART, this requires a release of information. In addition, youth often fail to make or keep these appointments. ATN 144 SMART has faced multiple challenges to enrollment, primarily difficulty obtaining VL and/or youth who are ineligible due to self-reported VL level.

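### DABS: the rule that an undetectable dried blood spot result needs no further step lacks the caveat that, at the protocol's own estimated limit, it cannot rule out a viral load of 200 copies/mL or more

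*Protocol*

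**What the plan says.** Section 7.0 (Sharing of Results with Subjects, Sub-Study) sorts DBS results into detectable and undetectable and does not define undetectable for DBS. For the undetectable group the rule is: "For those who had undetectable VL, no further step is needed". The detectable group is referred to SMART and elsewhere as needed. The paragraph then ends: "Participants will also be recommended to follow up with health care provider". It also says that phone and email templates will explain what the result means, and that the team gives results to nobody other than the participant.

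On the assay, Aim 4 of the sub-study (Section 1.0, repeated in the Study Summary) says: "Currently, the lower limit is estimated at 500 to 800 copies/mL". It adds that this falls short of the current 200 copies/mL definition. Section 2.0 gives the published basis: "Only two studies have found the lower detection limit to be 550 and 800 copies/mL". The same aim sets out to "evaluate the accuracy and lower limit of detection of a DBS". Section 5.0 names the collection kit and the assay but gives no DBS limit for that combination.

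On the threshold, Section 5.0 (Referral to ATN 144 SMART) says: "Subjects that produce an unsuppressed VL (≥ 200 copies/mL) could potentially join ATN 144 SMART as a subject".

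**The concern.** The aims acknowledge that DBS may not reach 200 copies/mL, but the rule for returning results does not carry that limitation through. A participant whose true VL lies between 200 and the DBS limit is unsuppressed by the trial's definition, yet falls in the group for which nothing further is required.

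The word undetectable also carries weight here. Section 2.0 describes the public health message that people with an undetectable VL do not transmit HIV. It also says that youth often miss appointments for conventional testing, so for some participants the DBS result may be the only recent VL. Because the team does not pass results to clinicians, a provider would not automatically see the result and qualify it.

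What is at stake is how well a participant understands their own result. No estimate, test or sample size in SMART or DABS depends on this sentence.

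**Working it through.** No figure in the plan needs reproducing. The check compares the stated limit with the stated threshold.

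Inputs:
- Estimated DBS lower limit, L: 500 to 800 copies/mL (Section 1.0, sub-study Aim 4; Study Summary). The two published values are 550 and 800 (Section 2.0).
- Threshold for unsuppressed VL, T: 200 copies/mL (Section 5.0, Referral to ATN 144 SMART).
- Planned sub-study enrolment: 50 (Study Summary; Section 11.0).

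For simplicity, treat L as a sharp cut, so that an undetectable result means only that VL is below L. It then excludes VL of T or more only if L is no greater than T. If L exceeds T, the undetected but unsuppressed range runs from T up to L. Its width is L − T, and the limit stands log10(L/T) above the threshold.

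| L (copies/mL) | L/T | log10(L/T) | L − T | Unsuppressed VL that may read as undetectable |
|---|---|---|---|---|
| 500 | 500/200 = 2.50 | 0.398 | 300 | 200-499 |
| 550 | 550/200 = 2.75 | 0.439 | 350 | 200-549 |
| 800 | 800/200 = 4.00 | 0.602 | 600 | 200-799 |

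L exceeds T throughout the stated range. The rule would be safe as written only if the limit achieved with this kit and assay were 200 copies/mL or lower, and the protocol does not say that it is.

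The follow-up sentence has two readings. If it applies to all participants, it sits awkwardly with the statement that nothing further is needed, but it does give the undetectable group a route to care. If it continues the sentence on detectable results, the undetectable group gets no advice. On neither reading does Section 7.0 say that an undetectable DBS result leaves VL of 200 or more open.

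The documents do not give the share of participants with VL between 200 and L, so no count can be derived. Planned enrolment of 50 is the only upper bound.

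**The case against.** The strongest defence is that the sentence describes staff actions. Beside the sentence on detectable results, it may mean only that the team has no referral to make, with no suggestion that participants are told nothing more is needed. That reading is reasonable, and it is why the harm is stated as possible. It does not remove the gap, because Section 7.0 still omits the caveat that the protocol's own aims call for.

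A second defence is that the matter is already handled. The closing sentence refers to participants in general, the templates must explain the result, and the revision history (version 5) lists a script for sharing VL results. All of this may be so. The script's text is not available, so it may already state the limit, and its content should not be presumed either way.

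A third is that 500 to 800 is a general estimate and the limit for this kit and assay may be better. That stands too, and it makes the gap conditional. It also means the protocol does not yet have the evidence that would justify the rule.

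A reader might go further in several ways that the documents do not support:
- *That participants were falsely reassured.* No result message is shown, and nobody is shown to have a VL in the gap.
- *That eligible youth were lost to SMART.* Section 9.0 lists low self-reported adherence as an alternative to the VL criterion, and no number is given.
- *That the script is out of date because the laboratory later changed.* The revision history is a summary, and its silence on a script revision proves nothing.
- *That SMART's assay rule is breached.* The statement "VL measurements using a level of detection ≥ 200 copies/mL will not be accepted" concerns VL results submitted for SMART assessments. It does not govern how DABS returns results to participants.

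**Conclusion.** The point holds as a minor, inexpensive correction. At the protocol's estimated DBS limit, which is 2.5 to 4 times the 200 copies/mL threshold (0.40 to 0.60 log10), an undetectable result cannot exclude an unsuppressed VL, and Section 7.0 attaches no caveat to it. The consequence is possible false reassurance, of unknown frequency, in at most the 50 planned sub-study participants. No SMART or DABS analysis changes.

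This rests on two assumptions: that the 500 to 800 estimate is relevant to the kit and assay used, and that the unseen script does not already supply the caveat. If the achieved limit proves to be 200 or lower, the concern about the result falls away. If the script already states the limit and advises follow-up, what remains is bringing the protocol text into line with it.

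**What to change.** In Section 7.0 (Sub-Study), replace the statement that nothing further is needed with wording such as:

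> *No study referral is needed. The result will be reported as below the DBS assay limit (stating the limit, or that it is not yet established), with an explanation that this does not confirm a viral load below 200 copies/mL.*

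State that the recommendation to follow up with a health care provider, including for routine VL monitoring, applies to all participants whatever their result. Then check the result-sharing script against this text and amend it if it differs.

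The fix should not add SMART screening triggered by a later provider VL. DABS participation ends with the interview and the referral offer comes at that point (Section 5.0). The sub-study has no described route for retrieving later provider results, and Section 2.0 notes that obtaining conventional results for research requires a release of information.

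The cost is one reworded paragraph and one script check, with no new study procedure. The message becomes slightly less reassuring, and some participants may have extra VL tests in usual care. These could bring co-pays: Section 20.0 makes SMART participants responsible for co-pays at provider visits for VL testing but expects DABS participants to bear no costs. The recommendation should therefore be worded as routine monitoring through usual care, not as a study test.
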